
or BT; 10-20% undergo PT. The urology clinic at PRINCIPAL INVESTIGATOR (LAST, FIRST, MIDDLE): [name] PCORI Research Plan: Research Strategy 9 the Hospital of the University of Pennsylvania (HUP) treats more than 60% of this group; the rest are treated at Presbyterian Medical Center and Pennsylvania Hospital. Additionally, UPHS has a proton therapy center, providing a unique opportunity to study this new technology. The Philadelphia Veterans Administration Medical Center (PVAMC) cares for 33,000 veterans in Philadelphia area and evaluates ~400 patients with newly diagnosed PCa each year. Fox Chase Cancer Center evaluates ~500 patients with newly diagnosed PCa each year. Together, UPHS, PVAMC, and Fox Chase Cancer Center provide care to socio-demographically diverse population of ~2,500 men newly diagnosed with PCa each year. Thus, our study sample requirement of 720 patients (33% of the available pool) can be fulfilled comfortably, as demonstrated by the successful recruitment for our earlier studies. Recruitment: Prior to study initiation, investigators will explain the study objectives to physicians who actively treat PCa at the UPHS, PVAMC, Fox Chase urology clinics. During a patient's initial visit, Drs. [name], [name], or [name] will briefly introduce the study to the patient. Each week, the research assistant will contact the participating physician offices to obtain contact information for those patients who have expressed an interest in the study. Potential participants will be contacted during their office visits, at which time those eligible may agree to participate and provide informed consent, request additional information and/or time to think or request to be contacted later. Patients who request to be contacted later will be sent study information, a consent form and a prepaid return envelope. Participants will discuss the consent form with research assistant prior to signing, at which time all questions will be answered. During enrollment, compensation of \$20 will be provided. Using a similar recruitment strategy in our prior PCa studies, we had achieved enrollment and retention rates of 85% or higher. The expected number of 60 participants in each treatment group (AS, RP, RALP, EBRT, BT or PT) will be achieved as follows: (1) each recruited participant randomly assigned to the conjoint analysis intervention group will meet with research assistant to complete the computer-based conjoint analysis tasks and other surveys before initiation of treatment or making a treatment decision; (2) after treatment decision is made, patients (both cases and controls) will be assigned to the appropriate group based on treatment; (3) this process will continue until we reach the required number of participants in each group. To achieve this, we may evaluate and obtain baseline data including conjoint tasks from patients in excess of the required 360 participant each in the intervention and control groups. Based on our prior prospective cohort studies, to fulfill sample requirement of 60 participant in each treatment group ($60 \times 2 \times 6 = 720$), allowing for attrition we expect to obtain baseline assessment including conjoint tasks for 800 participants (10% excess). The cohort that does not get assigned for further follow-up due to targeted group enrollment accrual will be analyzed to ensure comparability. D.2.2 Process of stratified randomization: We will recruit 720 participants stratified by three hospitals-UPHS, PVAMC, or Fox Chase Cancer Center (Figure 3). [name] will create randomization sequences for each hospital using a pseudo-random number generator with random blocking and will place the treatment assignments in sealed, opaque envelopes. All investigators, staff and referring physicians will be masked to the treatment assignment, except the research assistant who will open the envelope and notify participants of group assignment. Participants will be instructed not to reveal their group status to physicians or study personnel, except in case of emergency or if necessary for medical reason, which we believe to be unlikely. D.2.2.1 Conjoint analysis intervention The primary goal of patient-centered PCa care is to engage patients and their families in meaningful and thorough interactions with their healthcare providers to develop accurate and well-conceived treatment choice, using all available medical information appropriately, while also considering the medical, social and cultural needs and desires of the patient and family. It is important for providers to solicit patient preferences and not make assumptions about which treatment and associated side effects patients are more likely to prefer or feel is best for them. Results of conjoint analysis will be shared with the participants of the intervention group, family members, and treating physicians prior to treatment decision. D.2.2.2 Usual care controls: Participants from this group will receive usual care that consists of standard educational material about various treatment options. D.2.3 Data collection and follow-up: After obtaining informed consent, baseline data will be obtained in person prior to the initiation of treatment. Participants will meet with the research assistant to complete the PRINCIPAL INVESTIGATOR (LAST, FIRST, MIDDLE): [name] PCORI Research Plan: Research Strategy 10 computer-based conjoint analysis tasks. Patient identifiers will be removed to maintain data confidentiality. Only the PI will have access to the master files. For conjoint analysis, each participant will be asked to express his preference for attributes and attribute levels for active surveillance and five active treatments for clinically localized PCa (RP, RALP, EBRT, PT, BT) based on choice sets presented. The choices will vary based on the differing attributes of various treatments ascertained in prior work and focus groups. After pilot testing and refining the conjoint task in Phase 1, final attributes and levels will be used. Trade-offs

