
The following documents are currently attached to this item:

There are no documents attached for this item.

Analysis Plan

Analytic Methods General: The statistical analysis will proceed in three stages: First, we will check the data quality and carry out descriptive analyses of demographics and key outcome variables. Next, we will assess preferences using conjoint analysis and inferential analysis. For continuous outcome variables, we will check for homogeneity of errors using spread-vs.-level plots and will consider transforming variables that either are highly skewed or have variance that depends strongly on the mean. We will use methods based on general linear model (univariate and repeated-measures ANOVA, mixed models) to analyze uncensored continuous outcomes, such as generic and prostate-specific HRQoL, psychological wellbeing and satisfaction with care. For potentially censored outcome variables such as time to PSA recurrence, we will use Kaplan-Meier curves and Cox proportional hazard models. Poisson regression (zero-inflated) will be used for count data. We will use Bonferroni correction for multiple testing. We will use propensity-score and instrumental variable approach to minimize observed and unobserved bias within groups (i.e. intervention group and usual care control group). **Missing Data:** We will attempt to prevent missing data by ensuring that data collection is as complete as possible. Should there be substantial missing data, however, we will employ analysis and imputation methods to reduce bias and increase efficiency [279-282]. Based on the proportion of missing data, we will use complete-case analysis, or explore available techniques, such as standardized score imputation, simple means imputation, maximum likelihood model-based imputation, data augmentation, etc. [281]. When data are evidently non-missing at random, we will conduct explicit non-ignorable modeling and sensitivity analysis [278]. **Propensity score matching:** In observational studies, comparisons between treatment groups that do not adjust for factors associated with treatment choice may be biased. Propensity score technique offers a highly practical approach to address such bias [283]. Here, the probability of each participant being in the treatment arm (i.e., the propensity score), is estimated. Participants are sorted by their propensity scores; the sample is divided into strata based on estimated scores, the treatment effect within each stratum estimated and overall estimate computed by aggregating across strata in a weighted analysis. When the model for predicting treatment status includes all relevant covariates, within strata treatment groups will be balanced on all predictors and the overall comparison of treatment arms will have substantially lower bias. We will use a model relating PCa treatment (RP, RALP, EBRT, PT, BT or AS) to baseline factors [283-284]. To study the extent to which treatment groups are now matched, we will compare t-statistics for these covariates before and after adjusting for propensity score. This will be done separately for intervention group and usual care controls. **Instrumental variable analysis:** Another limitation of observational research is the strong potential for confounding bias, due to differences in comparison groups that are not reflected in the data (i.e., unobserved bias). The instrumental variable (IV) approach is useful in reducing this bias. This technique uses one or more observable factors that influence outcome only indirectly (the IV). This allows one to mimic randomization with different likelihoods of receiving a particular treatment [227, 285-291]. Physicians play an important role in patients treatment choice- a majority of the PCa patients report that their physicians recommendation was the most important factor in their treatment choice [11-12, 37-46, 51, 55-56, 60-64]. We will use specialty of the first physician (urologist, urologic oncologist, oncologist, radiation oncologist) who the patient saw during PCa diagnosis as an IV. We will explore other potential IVs, such as absolute distance between patients residence to the hospital where they will receive care (Hospital of University of Pennsylvania, Presbyterian Medical Center, PVAMC, Pennsylvania Hospital, or Fox-Chase Cancer Center). Validity of the IV(s) is assessed as following. First, we will use Pearsons correlation coefficient to examine the correlation between IV, primary exposure (treatment) and outcomes. We will then perform a partial F-test using a linear regression where treatment group is regressed on physician specialty along with patient attributes. For a valid IV, test statistic should be very high (e.g., physician specialty will strongly predict treatment after adjusting for covariates). Next, we will perform a partial F-test using a linear probability model in which HRQoL outcomes are regressed on specialty and patient demographic and clinical variables. For an IV to be valid, this test statistic should be very low. Finally, we will compare observable attributes across patient groups cared for by different physician specialty (initial). For the IV be valid, these groups should have comparable observable attributes. **Phase 1 Focus group analysis-development of conjoint task instrument:** The goal of focus groups is to identify attributes of PCa treatment that are most salient to localized PCa patients. This process includes following steps: (1) identifying and defining attributes; (2) assigning attribute levels; and (3) creating scenarios and choice sets. Attributes will be defined based on input from patient focus groups, literature, our prior research, and prior physician focus group. Once an attribute and its extreme values are defined, we will assign them appropriate levels. A large number of possible combinations of attributes and levels will preclude

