patients in decision (measured using CPS) using multi-nominal regression model to adjust for observed covariates. Then we will examine if these associations vary across intervention and usual care control groups. We then will repeat the model with other independent variables (decision conflict and trust). Next, we will test the association denoted by path c (direct effect of DCS, CPS, and trust on outcomes). For continuous outcomes (HRQoL, AUA-SI, MAX-PC, CES-D, SWD, and PSQ-18), we will compute area under the curve (AUC) for each measure for each patient. We will analyze AUC summaries with univariate linear models. In our main analysis we will analyze the series of functional status measures using linear mixed models that predict the outcome from time, independent variables and their interaction. We will repeat the analyses described for path c, this time by including treatment received in the models. We will test if the observed effects of DCS, CPS or trust on outcomes will be weaker after controlling for treatment. These analyses will be performed within and between groups (intervention and usual care controls). Specific Aim 3: Hypothesis: Prostate cancer patients in the intervention group undergoing conjoint analysis-value clarification exhibit improved treatment choice, satisfaction with decision, lower regrets, and improved objective and subjective outcomes. Analysis for Specific Aim 3 uses intent-to-treat approach: all randomized participants will be included regardless of whether they drop out of the intervention or study. Analysis will involve comparison of the primary outcomes between intervention and usual care control groups. Improved treatment choice is operationalized as the likelihood of low-risk PCa patients receiving active surveillance than active treatment, and will be compared between intervention and usual care control group. To allow for different trajectories of the outcome measures and to afford flexibility in making contrasts within participants over time and across participants, while simultaneously controlling for potential confounders, we propose the participant-specific or mixed effects linear model, in which the mean outcome depends on fixed covariates and random effects. The primary fixed effects will be indicators for intervention group and hospital. We will also stratify the analysis by type of treatment. The random effects represent the unobserved factors that lead to variation of the individual participants outcome. Random intercepts for each participant permit modeling of natural variation across participants at baseline. In addition, random slopes or random effects for the trajectory of each participant over time, allow for variation of each participant about a mean, overall trajectory across all participants. Although less robust to model misspecification, the mixed effects paradigm offers special flexibility in longitudinal data when exposures vary over time and when dropout and missed visits lead to unbalanced groups. The target of inference is the participant-specific response to treatment over time. At each time point of interest, we will estimate from the fitted model the difference from baseline in outcome for the treatment and control groups and test the difference between these differences. Both univariate and multivariate results will be reported in terms of Wald test, point estimates, and 95% confidence intervals. Specific Aim 4: Hypothesis 4: Prostate cancer patients whose treatment is more concordant with their values markers will experience improved subjective and objective outcomes. This specific aim s for intervention group only. We will analyze the association of the concordance between stated individual preferences and actual treatment received with objective (PCa recurrence and complications), subjective (HRQoL, psychological wellbeing, SWD, and satisfaction with care) outcomes, across treatment groups, adjusting for covariates. Association between the value markers (profiles) and measures of outcomes and personal and clinical characteristics: The value markers will be studied for their relationship with socio-demographic and clinical characteristics. We will also assess the association of value markers with outcomes. We will perform logistic regression with outcomes as the dependent variable and dummy variables for the utility-based profiles obtained earlier as independent variables. We will perform this evaluation with and without adjusting for patient attributes in the logistic model. For each case (adjusting and not adjusting for patient attributes), the evaluation of association between these profiles and outcomes will be based on a likelihood ratio test of the set of odds ratios corresponding to the dummy variables of the profiles. Additionally, we will perform a sequence of pair wise tests of comparisons of the profiles in terms of the proportion of type of treatment received based on the Holms multiple comparisons approach. This procedure is hierarchical in that it will identify the utility-based profile at the start of the process before making other comparisons, thus protecting the Type I error from additional comparisons. Specifically, Holms approach tests each pair-wise comparison in ascending order of p-values. Successively larger p-values have less rigorous alpha. The sequential Holm tests terminate after the first non-significant comparison so no subsequent comparison is significance. Concordance and its assessment: Understanding and respect for the patients preference and values is the main aspect of concordance [69, 73]. Thus a first step in concordance involves the physician extracting and understanding the patients view, followed by an agreement between the physician and patient regarding a management plan that integrates their views. There exist many definitions of concordance. For the purpose of this study, we operationalized concordance as agreement between a patients value markers and the attributes (or characteristics) of the treatment that

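### The propensity-score text describes a two-group method but applies it to six treatments, so the balance it promises does not hold for the six-group comparison

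*Combined protocol and SAP*

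**What the plan says.** Everything on the method is in the Analysis Plan under Propensity score matching. The score is defined for two groups: "the probability of each participant being in the treatment arm (i.e., the propensity score), is estimated". Its use is then described: "Participants are sorted by their propensity scores; the sample is divided into strata based on estimated scores". A treatment effect is estimated in each stratum, and the stratum estimates are combined by weighting. Provided the model contains all relevant covariates, the plan states that "within strata treatment groups will be balanced on all predictors and the overall comparison of treatment arms will have substantially lower bias".

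The study-specific sentence follows: "We will use a model relating PCa treatment (RP, RALP, EBRT, PT, BT or AS) to baseline factors". For the balance check, "we will compare t-statistics for these covariates before and after adjusting for propensity score". Finally, "This will be done separately for intervention group and usual care controls".

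The plan does not give the form of the six-treatment model, how its fitted probabilities become a score that can be sorted, the number of strata, or the treatment pairs that the t-statistics compare. The heading speaks of matching, whereas the text describes stratification.

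**The concern.** With two groups, one probability carries all the information on treatment assignment that the covariates provide, and stratifying on it balances the groups. With six treatments each man has six probabilities that sum to one, so five are free. Sorting on one of them leaves the other four free to vary within a stratum.

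Comparisons between treatments are a planned output. Recruitment is organised "to fulfill sample requirement of 60 participant in each treatment group" in each arm, the Accrual section claims adequate power for differences between treatment groups, and Potential Study Benefits promises assessment within and between them. If the text were followed as written, differences between, say, EBRT and surveillance could be presented as adjusted while much of the covariate imbalance between those men remained.

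**Working it through.** **Inputs from the protocol.** Six treatments, 60 men per treatment per arm, two arms: 60 × 2 × 6 = 720, which reproduces the planned total. Each arm has 720 / 2 = 360 men. There are 6 × 5 / 2 = 15 treatment pairs. The plan gives no figure for covariate balance, so there is none to reproduce.

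**Why one score is not enough.** Let e_k(x) be the probability of treatment k for a man with covariates x, and take treatment 1 as the index. Among men with e_1(x) = c, let f(x | c) be the covariate density. The density among those who received treatment k is proportional to f(x | c) × e_k(x).
- For treatment 1, e_1(x) = c is constant, so the density is f(x | c).
- For the other five pooled, the factor is 1 − c, also constant, so the density is again f(x | c). The index treatment is balanced against the rest pooled.
- For any other single treatment, e_k(x) still varies with x. Its covariates need not match those of treatment 1 or of any other treatment.

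**How much is left.** This was simulated with assumed inputs: 60,000 men per run, 12 runs per setting, six equal treatment groups, multinomial-logit choice on standard-normal covariates, and quintiles of one treatment's true probability. In the first five rows the coefficients are random normal with SD 0.3 or 0.6. In the last row the six treatments are ordered along one common dimension, at two strengths. The residual is the length of the covariate mean-difference vector after stratification divided by its length before. Ranges cover the two selection strengths.

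| Assumed drivers of choice | Pairs among the other five | Pairs with the index treatment | Index vs rest pooled |
|---|---|---|---|
| 1 covariate | 14–35% | 14–34% | 9–19% |
| 2 independent | 69–73% | 45–46% | 11–15% |
| 3 independent | 85–87% | 53–54% | 11–12% |
| 5 independent | 93% | 58–65% | 11–12% |
| 8 independent | 95–97% | 55–57% | 11–14% |
| 5 acting along one dimension | 13% | 12–14% | 11–12% |

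A separate score for each pair, also in quintiles, left 11–12% in every setting.

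**At the planned size.** With 360 men, fitted multinomial scores and assumed coefficients, quintiles of one score left about 45–96% among the other five treatments. Generalised overlap weights left about 11–36% over all pairs. With three to five covariates, the effective sample under overlap weights was about 25–39 of the 60 men per treatment.

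**Cell sizes.** If five strata are assumed, 60 / 5 = 12 men per treatment per stratum on average within an arm.

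**The balance check.** A t-statistic mixes imbalance with sample size. If the effective sample falls from 60 to 25 per group, t shrinks by √(25/60) = 0.65 with no change in imbalance. A smaller t after adjustment is therefore not evidence of better balance.

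**The case against.** The strongest reply is that the two-group wording is a general account of the technique, and that the study-specific sentence names all six treatments. That sentence is compatible with a multinomial model or with pairwise scores, and a t-statistic suits pairwise use. This stands in part: no text says that men will be sorted on the RP score or on any other single treatment's score. But the general account is the only procedure given, and the balance promise belongs to it.

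A reader might infer that confounding between treatments is left almost untouched. The documents do not support that. The residual is near-complete only when several independent factors drive choice, and the plan does not quantify selection. The protocol does point to more than one driver: age (Background A.1), physician specialty (Conceptual Framework) and access to a proton centre at one site (Participant availability). It does not show how strongly they act or whether they share a dimension. Nor would it be right to say that one score balances just two treatments. It balances one against the rest pooled, and pairs that include the index treatment can themselves stay imbalanced.

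It is also fair that other adjustment is planned. Aim 2 models treatment received "using multi-nominal regression model to adjust for observed covariates", and Aim 4 adjusts for covariates. An instrumental variable is proposed too, but the named instrument has four specialties, hence at most three independent contrasts where six treatments need five; distance is only to be explored. The balance check might expose residual imbalance, although no pairs and no consequent action are stated.

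**Conclusion.** The point holds in a limited form. The written method is for two groups, the exposure has six levels, and the stated balance does not follow for the six-group comparison. That conclusion needs no simulation. Its size does: about 13% to 97% of the imbalance among the non-index treatments remains, depending on the assumed number and independence of the drivers of choice, the selection strength and five strata.

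A reader might go further and conclude that the trial's main comparison, or every reported treatment difference, would be biased. The documents do not support this. Aim 3 compares randomised arms by intention to treat, and the propensity step is applied within arms. The models for Aims 2 and 4 carry their own covariate adjustment. For surveillance against all active treatment pooled, one score would be sufficient. What needs correcting is the adjusted comparison among the six treatments and the assurance attached to it.

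**What to change.** Replace the sort-and-stratify text with one multinomial propensity model for the six treatments, fitted separately by arm as planned or jointly with randomised arm as a covariate. Compare treatments with generalised propensity weights (overlap weights or trimmed inverse-probability weights) and robust standard errors. Pairwise scores declared in advance are an acceptable alternative; the plan should then name the pairs, give the number of strata and acknowledge that each pair describes a different population.

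Replace the t-statistics by standardised differences over all 15 pairs, before and after adjustment. Delete the balance sentence, or limit it to the balance actually shown.

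The cost is wording and modest programming. Precision falls, as the effective sample sizes above show. Overlap weights also change the question, because they target men who could plausibly have had any of the compared treatments. Model size needs care: the confounder section (D.2.4.4) lists about 15 variables (stage, grade, histology, Gleason score, comorbidity and ten demographic or history items). Each needs at least five slopes, so 15 × 5 = 75 slopes for 360 men if fitted by arm. This favours the joint fit or a shorter covariate list fixed in advance.

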size based on the observed differences in outcomes such as HRQoL (SF-36 and prostate cancer index, PCI) and cost of PCa care across groups. The primary outcome is HRQoL as measured by the SF-36 and PCI sub-scales. A change of 5 to 9 points on PCI is clinically meaningful [272]. Similarly, a difference of 7 points or more on the SF subscales is considered clinically meaningful [272, 275, 301]. Based on our prior research and that of Litwin et al [253, 272], the standard deviations for the PCI and SF-36 scales in samples of men with PCa mostly range from 8 to 14; hence standardized differences (SDs) of $7/14=0.5$ to $7/8=0.87$ will be clinically relevant. The power calculations for Aims 2-4 assume availability of 720 participants who are eligible for randomization into one of the two intervention groups. We assume a conservative intra-class correlation of 0.3 and 4 follow-up measures per subject. The sample size is adjusted to accommodate a 10% missing or dropout rate by 24 months based on rates over a similar period of time in previous studies [272, 275, 301]. We assume 80% power and two-sided level of significance of $\alpha = 0.05$. We have 80% power to detect a 1.2 point difference in PCI or SF-36 sub-scale. Within treatment type, the sample size is reduced to 60 per intervention arm. We have 80% power to detect a 3.0 point difference in sub-scale with 60 patients in each arm. Thus, we will have adequate power to detect differences between treatment groups [302]. Power for identifying utility based profiles and outcomes: We analyzed the levels of power for differences in outcomes between profiles defined by latent classes of attributes-specific utilities with a conservative allocation of subjects to each profile (25 in one vs. 10 in other profile) and less conservative allocation (35 in one profile vs. 35 in other profile) using a logistic model based comparison for a binary outcome (e.g. recovery of baseline HRQoL) with a 2-sided alpha of .0125 (Holms adjustment profiles). In the first allocation, the group difference of 0.56 yields 80% power; for the second allocation an effect size of 0.42 corresponds to power of 90. Thus, with our anticipated effect size of 0.51, we will have adequate power with $n=60$ in each group. (Adjusting for patient characteristics may reduce the effect sizes of the differences between profiles.)

Key inclusion criteria

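### Propensity-score balance across the six treatments is judged only by covariate t-statistics, which depend on sample size as well as imbalance; standardised mean differences would be better evidence

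*Combined protocol and SAP*

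**What the plan says.** The passage is in the Combined protocol and SAP, Analysis Plan, under Propensity score matching. The method is stratification: "the sample is divided into strata based on estimated scores, the treatment effect within each stratum estimated", and the stratum estimates are then combined with weights. The exposure has six levels: "We will use a model relating PCa treatment (RP, RALP, EBRT, PT, BT or AS) to baseline factors". The balance check is introduced by its purpose, "To study the extent to which treatment groups are now matched", and consists of one comparison: "we will compare t-statistics for these covariates before and after adjusting for propensity score". The next sentence adds: "This will be done separately for intervention group and usual care controls".

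The plan does not give the number of strata. It does not say whether the adjusted t-statistic is computed within each stratum or pooled over strata, which of the six treatments are contrasted, or what value would count as balanced. For the propensity score it names no standardised difference or overlap check. The later comparison of observable attributes in the same section concerns the groups defined by the instrumental variable (specialty of the first physician), not the propensity score.

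The group size comes from the power text under Accrual, "Within treatment type, the sample size is reduced to 60 per intervention arm", and from the recruitment text in the Design and Subject recruitment sections, "to fulfill sample requirement of 60 participant in each treatment group".

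**The concern.** Balance is a property of the groups in hand: how far apart the covariate means are, relative to their spread. A t-statistic answers a different question, namely whether that gap is large relative to its sampling error. With about 60 men per treatment per arm the sampling error is large, so a covariate can differ by a meaningful amount and still give an unremarkable t. If the adjustment step also divides the sample, t can fall because each comparison contains fewer men, and that fall can be misread as better balance.

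At stake are the comparisons between treatments within each arm, which are observational. The Background itself says that age strongly influences which treatment a man receives, so real confounding is expected. A check that cannot separate lost precision from gained balance gives poor guidance on whether the propensity adjustment has worked.

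**Working it through.** **Inputs from the document.** There are 60 men per treatment per arm, six treatments and two arms: 60 × 2 × 6 = 720, which reproduces the planned total. Within one arm, one treatment against the other five is 60 v 300, and a pairwise comparison is 60 v 60. The document gives no figure for the balance check itself.

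**Assumptions, not in the document.** The number of strata (five, with three and ten as a range), treatments split evenly across strata, and the illustrative standardised differences d of 0.2, 0.3 and 0.5. Significance is taken as two-sided 0.05, the level used in the plan's power text.

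**Formula.** For a standardised mean difference d, the expected t is approximately

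t = d × √(n1·n2/(n1+n2)), which for equal groups of n is d × √(n/2).

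**Step 1: adjusted t computed inside a stratum, imbalance unchanged at d = 0.20, five equal strata.**

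- One treatment v the rest, 60 v 300: 0.20 × √50 = 1.41. In one stratum, 12 v 60: 0.20 × √10 = 0.63.
- Pairwise, 60 v 60: 0.20 × √30 = 1.10. In one stratum, 12 v 12: 0.20 × √6 = 0.49.

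Each is a fall of 1 − 1/√5 = 55% with no gain in balance. With k equal strata the fall is 1 − 1/√k: 42% for three and 68% for ten.

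At d = 0.20 neither starting value is significant, so no significance verdict changes. At d = 0.50 one does:

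| Pairwise comparison | Expected t at d = 0.50 | Chance of a non-significant result |
|---|---|---|
| 60 v 60 (unstratified) | 2.74 | 22% |
| 20 v 20 (3 strata) | 1.58 | 66% |
| 12 v 12 (5 strata) | 1.22 | 78% |
| 6 v 6 (10 strata) | 0.87 | 88% |

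**Step 2: adjusted t pooled over strata, imbalance unchanged.** For five strata of 12 v 60, the variance of each stratum difference is 1/12 + 1/60 = 0.10 in SD units. The equally weighted average has variance 0.10/5 = 0.02 and standard error 0.141, so t = 0.20/0.141 = 1.41, exactly as before stratification. For five strata of 12 v 12 the pooled t is likewise 1.10.

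When the score does separate the groups, the strata become uneven and some precision is lost. This was simulated with 60 v 60, five strata and 1,500 runs, using a covariate that the score cannot balance and d = 0.50. The mean pooled t was 2.72 (2.77 before) with no separation and 2.37 (2.79 before) with a separation of 1 SD. The remaining difference was still about 0.5. The mean within-stratum t in the same runs was 1.13 to 1.26.

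**Step 3: what a non-significant t shows at full size.** At 60 v 60 the smallest observed difference that reaches significance is 1.98 × √(2/60) = 0.36. A true difference of 0.3 gives an expected t of 0.3 × √30 = 1.64, and the noncentral t distribution puts the chance of a non-significant result at 63%. This weakness is present without any stratification.

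**Step 4: what a standardised-difference threshold could achieve here.** The standard error of a pairwise standardised difference at 60 v 60 is about √(2/60) = 0.18. Among six groups formed by perfect randomisation, the expected range of the six means is 2.53 standard errors of a single mean, so the expected maximum pairwise difference is 2.53/√60 = 0.33. It falls below 0.10 in about 0.6% of cases. A hard 0.10 limit on the maximum pairwise difference would therefore flag nearly every covariate by chance after stratification.

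**The case against.** The strongest reply is that the large fall in t rests on a reading the plan does not state. The text speaks only of adjusting for the score, close to a description of an estimator aggregated over strata, and a pooled t is at least as natural a reading. On that reading Step 2 shows little or no fall from sample size. This stands, and the 55% figure must stay conditional on within-stratum computation and on five equal strata.

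A reader might infer that the plan lets confounded groups be formally passed as matched. The document does not support that: it sets no cut-off and describes the comparison as a way to study the extent of matching. A misleading impression of balance is possible, but it is not a written rule.

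A reader might also infer that the propensity method is built for two groups although there are six. The sentence about being in the treatment arm introduces the technique in general terms, and the sentence after it relates all six treatments to baseline factors. Only the form of that six-level model is left unstated.

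Finally, the consequences are limited. Aim 3 is analysed by intention to treat. Aims 2 and 4 adjust for covariates directly, and an instrumental-variable analysis is also planned. All of this stands. None of it makes a t-statistic a good measure of balance, and the Step 3 result does not depend on the reading chosen.

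**Conclusion.** The point holds in a limited form. The only propensity-score balance check in the plan mixes imbalance with sample size, so a small or reduced t is weak evidence that the treatment groups are comparable. If the adjusted t is within-stratum, t falls by 55% at unchanged imbalance (five equal strata assumed; 42% to 68% for three to ten). If it is pooled, the fall is nil to small: 2.79 to 2.37 in the worst case tried. Under either reading, even the undivided 60 v 60 comparison misses a true standardised difference of 0.3 about 63% of the time.

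The number of strata and the sizes of imbalance are assumptions. The 60 per treatment per arm is the plan's target. The point concerns the observational treatment comparisons only and is a minor improvement. The randomised comparison of intervention with usual care in Aim 3 does not depend on it.

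**What to change.** Replace the t-statistic comparison with standardised mean differences for each baseline covariate, before and after adjustment, pooled over strata with the same weights as the effect estimate. Report them within each randomised arm, either for each treatment against the others or pairwise, from the six-level treatment model the plan already names. State which contrasts are used and how many strata are formed.

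Include in the outcome model any covariate with material residual imbalance. Use 0.10 as a guide rather than a pass/fail limit, given the 0.33 maximum expected from chance at 60 per group.

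The cost is a few sentences in the Analysis Plan and a different summary table from the same fitted model. No extra data or participants are needed. A move to multinomial weighting would be a new analysis and is not required.
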